# 11.2.3 Safety

The frequency of each adverse event will be summarized by seriousness, severity and by relationship to the device. Since some subjects may report the same event several times (e.g., headache), the first occurrence of the worst reported case of the event will be used for the purpose of analysis. Refer to the User Guide for full list of expected adverse events.

#### 11.3 **Analysis Cohorts**

Different groups of subjects, or Cohorts, will be identified depending on the type and extent of analysis being performed. These may include but are not limited to the following:

## 11.3.1 Screening Cohort

All subjects who are screened for the study will be included in the Screening Cohort. Only an accounting of the numbers of subjects screened in the study, plus the reasons given for subjects not enrolled in the study will be performed on this Cohort.

# 11.3.2 Safety/ITT (Intent to Treat) Cohort

All subjects who are randomized are included in the Safety/ITT Cohort. Subjects are analyzed in the treatment group they are randomized to.

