**Table 3. Schedule of Assessments** 

Table 5. Schedule of Assessments							
	Visit 1 / Screening	Visit 2 / iovera° Treatment	Visit 3 / DAY OF TKA (Day 0)	Visit 4 / 2 Weeks Post-op	Visit 5 / 4 Weeks Post-op	Visit 6 / 6 Weeks Post-op	Visit 7 / 12 Weeks Post-op
Assessment Informed Consent	X						
	X	v					
Eligibility	X	X					
Medical history Concomitant medication	X	A					
assessment	X	X	X	X	X	X	X
Prior/Concurrent Therapy	X	X		X	X	X	X
Randomization*		X					
Study Treatment		X X X X					
Physical Exam		X					
Vital signs	X	X					
Knee Circumference		X					
PROMIS Questionnaire	X			X	X	X	X
WOMAC Questionnaire	X			X	X	X	X
SF-36	X			X	X	X	X
NRS for Pain	X			X	X	X	X
Work Status Questions	X			X	X	X	X
Subject Satisfaction Questions						X	X
Assessment of Blind		X		X	X	X	X
Physical Performance Measures	X			X	X	X	X
Pain Medication Accountability				X	X	X	X
AE/SAE Assessment		X	X	X	X	X	X
Photographs (if applicable)		X		X	X	X	X

\* Randomization occurs after the subject has met eligibility criteria and prior to or at Visit 2

Follow-up visits generally consist of the following:

- The Investigator or designee assesses the occurrence of health status changes and adverse events since last study visit;
- The Investigator or designee determines whether any changes in daily medications have occurred;
- The Investigator or designee performs drug accountability (pill counts) of postoperative outpatient opioid medication and re-dispenses unused opioid medications to subjects after use. The Investigator or designee records other over-the-counter concurrent pain medication use and pain relief therapies used per subject report;
- The Subject completes a WOMAC questionnaire, an SF-36 questionnaire, PROMIS questionnaire, Work Status Questions, Satisfaction questions (Visits 6 and 7 only),

self-assessment of the blind, and reports NRS for Pain when standing from a seated position;

• The Investigator or designee performs Physical Performance Measures (Range of Motion, 30 Second Chair Test and 40 Meter Walk Test).

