#### 11. STATISTICAL METHODOLOGY AND ANALYSES

#### 11.1 Introduction

This is a prospective, randomized, sham-controlled, multi-center, post-market trial to evaluate the iovera° device in treating pain associated with total knee arthroplasty (TKA). The study is designed to investigate whether iovera° treatment prior to TKA decreases cumulative patient opioid use over the course of 6 weeks following TKA while maintaining similar levels of pain relief.

The study will also investigate whether there is a relationship between patients treated with iovera° and length of hospital stay; patient reported pain and function as measured by WOMAC; patient satisfaction; and improved physical rehabilitation as measured by functional performance measures and range of motion.

The primary safety endpoint is the onset of device-related adverse events through twelve-weeks after TKA surgery. The primary measure of effectiveness is the Total Daily Morphine Equivalent (TME) of pain medications used from Day of Discharge to the 6-week follow-up visit. In addition. Change from Baseline in WOMAC Pain at the 6-week follow-up visit will be evaluated as a secondary endpoint. A variety of secondary effectiveness endpoints, including performance and pain assessments, will be measured.

Up to 8 study sites within the United States will screen a sufficient number of subjects to ensure that 150 subjects (Randomized 1:1 to approximate 75 Active Treatment subjects plus 75 Sham Treatment subjects) will be randomized and treated.

Subjects will be randomized either to receive therapeutic treatment with the iovera° treatment or to receive a sham treatment with the iovera° treatment, using a balanced 1:1 active-to-sham randomization stratified by Study Site.

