#### 12. ADVERSE EVENTS

The study Investigator and Coordinator will evaluate, characterize and record in the eCRF all adverse events (AEs) occurring in all subjects from the initiation of study treatment to study exit (or premature withdrawal). Device or procedure related AEs will be followed until resolution. AEs may be reported spontaneously by the subject or detected by the Investigator or coordinator. AEs should be evaluated for diagnoses not just symptoms (i.e., "angina", not "chest pain").

AEs may be either spontaneously reported or elicited during questioning and examination of a subject. All AEs must be completely recorded within the Subject's source documentation. All AEs will be evaluated by the Investigator for relationship to the ioverao device and to the treatment.

In addition to verbatim terms, the Sponsor will categorize all AEs using MedDRA preferred terms (PT) and system organ classes (SOC). Analysis will report both verbatim and MedDRA terms.

Adverse events (AEs) will be assessed continuously from the initiation of study treatment through study exit. Per ISO14155:2011, an AE is any untoward medical occurrence, unintended disease or injury, or untoward clinical signs in subjects, users or other persons, whether or not related to the investigational medical device. An AE can arise from any use of the device (e.g., off-label use, use in combination with any drug) and from any route of administration.

Timely and complete reporting of all AEs assists the Sponsor in identifying any untoward medical occurrence, thereby allowing:

- 1) protection of the safety of study subjects;
- 2) a greater understanding of the overall safety profile of the device;
- 3) recognition of device-related ill effects;
- 4) appropriate modification of study protocols;

-

<sup>4 Definition from ISO14155:2011

- 5) improvements in study design or procedures; and
- 6) adherence to worldwide regulatory requirements.

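### Section 11.3.2 makes all randomized subjects, analysed as randomized, the safety cohort, although adverse events are collected only once treatment starts: a minor mismatch that is nearly free to remove

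*Protocol*

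**What the plan says.** All references are to the protocol.

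- **Cohort (11.3.2).** Safety and ITT are one set, and the arm is the assigned one: "All subjects who are randomized are included in the Safety/ITT Cohort. Subjects are analyzed in the treatment group they are randomized to". No separate set of treated subjects is defined.
- **Endpoint (11.1).** "The primary safety endpoint is the onset of device-related adverse events through twelve-weeks after TKA surgery".
- **Safety summary (11.2.3).** "The frequency of each adverse event will be summarized by seriousness, severity and by relationship to the device". No other denominator is named.
- **Collection period (12).** Adverse events are those "occurring in all subjects from the initiation of study treatment to study exit". The note under Table 5 sends changes between screening and the start of treatment to medical history.
- **Timing of randomization (Table 3 footnote).** "Randomization occurs after the subject has met eligibility criteria and prior to or at Visit 2". Section 10.5 has eligibility reconfirmed at Visit 2, before the device is used.
- **Assigned versus received treatment (11.3.3).** The Per-Protocol Cohort is limited to subjects who got their assigned treatment, so the protocol allows that some may not.
- **Tips (9.1).** Active and sham Smart Tips look the same, and the lights and sounds of the device are the same.

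**The concern.** An ITT set and a safety set serve different purposes. Keeping every randomized subject in the assigned arm protects the effectiveness comparison. Applied to harms, the same rule can include people who were never exposed and can attribute an event to a treatment the subject did not receive.

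Here the rule does not fit the protocol's own collection period. A subject who is randomized and then not treated has no period in which an adverse event can be recorded, yet stays in the denominator of the primary safety endpoint. Such a subject can arise. Screening may be up to 30 days before, treatment falls in the last 7 days before surgery, and some exclusions can newly apply in between, such as recent anticoagulant use or a wound or skin problem at the treatment site. Anyone randomized ahead of Visit 2 could fail the re-check.

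Separately, identical-looking tips mean a mix-up would not be noticed during treatment. Under 11.3.2 a freezing-related event in a sham-assigned subject who received an active tip would be reported as a sham event.

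What is at stake is the accuracy of the reported device-related event rates and of the contrast between arms.

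**Working it through.** **Stated figures.** The protocol gives no event rate, no number untreated, no number given the wrong tip, and no sample size or precision for safety, so there is no safety figure to reproduce. The one input from the document is the arm size: 150 randomized 1:1 gives 75 per arm (11.1, 11.10). Everything else below is assumed and shown as a range.

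**1. Untreated subjects.** Let p be the event rate among treated subjects in an arm and u the number randomized to that arm but not treated. Under 11.3.2:

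reported rate = p × (75 − u) / 75

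The relative reduction is u/75, whatever the value of p.

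| u (assumed) | Factor | Relative reduction | An assumed 10% is reported as |
|---|---|---|---|
| 0 | 1.000 | 0% | 10.0% |
| 1 | 74/75 = 0.987 | 1.3% | 9.9% |
| 2 | 73/75 = 0.973 | 2.7% | 9.7% |
| 4 | 71/75 = 0.947 | 5.3% | 9.5% |
| 5 | 70/75 = 0.933 | 6.7% | 9.3% |
| 8 | 67/75 = 0.893 | 10.7% | 8.9% |

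For scale, 11.10 allows up to 10% (0.10 × 75 = 7.5 per arm) for early withdrawal and missing primary data together. The last row would need the whole allowance, and slightly more, to be untreated subjects.

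**2. Wrong tip.** Let pA and pS be the true rates with active and sham tips. Suppose k subjects in each arm receive the other arm's tip:

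- reported active rate = ((75 − k) × pA + k × pS) / 75
- reported sham rate = ((75 − k) × pS + k × pA) / 75
- reported difference = (pA − pS) × (1 − 2k/75)

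For k = 1 the factor is 1 − 2/75 = 0.973, a shrinkage of 2.7% relative. With assumed pA = 20% and pS = 5% (true difference 15.0 points):

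| k per arm (assumed) | Reported active | Reported sham | Reported difference |
|---|---|---|---|
| 0 | 20.0% | 5.0% | 15.0 points |
| 1 | 19.8% | 5.2% | 14.6 points |
| 2 | 19.6% | 5.4% | 14.2 points |
| 5 | 19.0% | 6.0% | 13.0 points |

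**3. Direction.** Untreated subjects always lower the rate of the arm they are in. Their effect on the contrast depends on where they fall. Equal numbers in both arms leave the rate ratio unchanged and shrink the difference by the factor in the first table. Swapped tips always pull the two rates together, which makes the device look safer only if pA exceeds pS. If the rates are equal, swaps change nothing.

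**The case against.** The strongest reply is that the mismatch is one of convention with no shown consequence.

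- **Few untreated subjects are likely.** Table 3 places randomization at Visit 2, screening and treatment may be on the same day, treatment is a single procedure, and 11.1 and 11.10 plan for 150 subjects both randomized and treated. This stands as a reason to expect a small effect. It does not cure the definition, because an enrolment target does not determine who is in the cohort.
- **Nothing turns on it.** Section 11.2.3 is descriptive. No safety test, margin or success rule is given, and effectiveness success is judged in the Per-Protocol Cohort. Every event is still recorded and assessed, and a reader with full disposition counts could recover the treated denominator. This stands, and it limits the severity.
- **No tip swap is suggested anywhere.** This also stands. Section 9.4 attributes the common local effects to needle passage, cooling and local anesthetic together. The needle and the anesthetic are the same in both arms, so a wide gap in event rates cannot be presumed.
- **The statistical analysis plan could add a cohort.** Section 11.3 leaves the list open. That is so, but 11.3.2 does more than stay silent: it assigns safety to the all-randomized, as-randomized set, and 11.9 also says all randomized patients enter all analyses.

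A reader might infer that the safety results are materially biased in the device's favour, for example that an active rate of 40% would be reported as 37.3% (40% × 70/75). The documents do not support that. Both the 40% and the five untreated subjects are assumptions, and the effect is zero if everyone is treated with the assigned tip.

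**Conclusion.** The point holds as a minor one. The protocol's safety denominator does not match its own period of adverse event collection, and its grouping rule can credit an event to a treatment the subject did not receive. The size is about 1.3% relative per untreated subject in an arm of 75 (0% for none, 6.7% for five) and about 2.7% relative off the risk difference for one swap in each arm.

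These figures rest on arms of exactly 75, on assumed counts, and on untreated subjects contributing no events, which follows from section 12. For swaps they also rest on the event rate following the tip used. Neither the number of such subjects nor the event rates can be taken from the protocol. The effect is probably small, and no stated conclusion depends on it. The reason to act is that the correction costs almost nothing.

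**What to change.** Split section 11.3.2 into two definitions:

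- **ITT Cohort:** all randomized subjects, analysed as randomized.
- **Safety Cohort:** all subjects in whom study treatment was started, grouped by the Smart Tip actually used.

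State in 11.2.3 that adverse event frequencies use the Safety Cohort. Change the reference to the combined cohort in 11.3.5 to the ITT Cohort, and bring the sentence in 11.9 on including all randomized patients into line.

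The grouping needs the tip type for each subject. Section 13 requires receipt, use and disposition of devices to be tracked, and 10.4 has the assignment recorded. Neither says that the type of tip used is tied to the individual subject, so it should not be assumed that this is already captured. Add that link to the device accountability records, held so that it does not unblind the treating investigator or the subject.

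The cost is a few lines of text and one linked item in existing records. No extra subjects or visits are needed.

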## 11.3.3 Per-Protocol Cohort

The Per-Protocol Cohort is defined as the group of subjects who are randomized in the study, who receive the treatment they are randomly assigned to receive, and who complete their 6-week visit without any major protocol deviations.

# 11.3.4 Cohort for Primary Endpoint

The objective for the primary Effectiveness endpoint needs to be met for the study to be a The analysis of the primary Effectiveness endpoint, Total Daily Morphine Equivalent, will be made using the Per-Protocol Cohort.

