# 10.7.1 Visit 4/2 Weeks Post-op (14 ±3 Days), Visit 5/4 Weeks Post-op (28 ±5 Days), and Visit 6/6 Weeks *Post-op (42 ±5 Days)*

Subjects will be evaluated and data collected per the schedule of events. Any changes in concomitant medications/concurrent procedures will be documented. Any anticipated observations, adverse events, adverse device effects and/or SAE/UADE/USADE will be assessed and documented. Photographs may be taken of the treatment area.

The Subject will complete a WOMAC questionnaire, NRS for Pain when standing from a seated position, PROMIS questionnaire, and SF-36 questionnaire. Subjects will be asked to assess their treatment assignment (the blind).

Subjects will answer Satisfaction questions at Visit 6.

The subject will complete the Physical Performance Measures in the following order under supervision of the investigator or designee:

- Active Range of Motion
- 40 Meter Walk Test
- 30 Second Chair Test

Detailed instructions for the conduct of these performance measures are included in the Study Operations Manual. Assistive/ambulatory device usage and work status will also be assessed.

Utilization of healthcare services post-discharge, or since the previous follow-up visit, will be assessed. Subjects will be asked to report any Secondary Surgical Interventions, Emergency/Urgent care visits, Unscheduled physician office visits, and other healthcare services used since their last study visit. Investigators will also record any additional or unscheduled services performed at follow-up visits (examples include knee aspiration, unscheduled x-ray, other unscheduled diagnostic procedures, etc.).

Subjects will be asked to bring all prescription opioid bottles to all study follow-up visits. A pill count will be completed by the study coordinator, or designee, and opioid medication will be redispensed to subjects.

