# 11.2 Study Endpoints

## 11.2.1 Primary Effectiveness Endpoint

The primary effectiveness endpoint is the cumulative consumption of opioids from the time of hospital discharge to 6 weeks post-TKA Surgery. Opioid consumption will be converted to morphine equivalents and subject consumption will be verified by pill count at follow-up visits. The cumulative morphine equivalent will be divided by the number of days to provide the Total Daily Morphine Equivalent (TME) for the subject.

The difference in the average TME between the two treatment groups will be calculated as Active TME average - Sham TME average, such that a positive difference indicates that the Active Treatment Group had a larger average TME than the Sham Treatment group, while a negative value indicates the opposite. A negative difference between treatment groups reflects a positive outcome for the study.

A superiority hypothesis test using the two-independent sample t-test will be used to statistically evaluate the difference in the average TME between the two treatment groups. A confidence interval for the difference in the average TME between the two treatment groups will be provided to assist in the interpretation of the results.

The Primary Effectiveness Study Objective is met when the average TME for the Active Treatment group is less than the average TME for the Sham Treatment group, and the resulting ttest is statistically significant using a one-sided  $\alpha = 0.025$  level of statistical significance

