# 11.3.5 Cohort for Secondary Endpoint

The Secondary Endpoint, Change in WOMAC Pain, will be made using the Per-Protocol Cohort. Analyses for all other secondary endpoints will be repeated using the Safety/ITT Cohort and the Per-Protocol Cohort

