#### 11.5 **Handling of Dropouts or Missing Data**

All endpoints will be analyzed "as-is" without any special data imputation methods used to replace missing data. Consequently, subjects missing results for a specific analysis will be excluded from that analyses.

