# 11.9 Sensitivity Analyses

No imputations for missing data will be made for the Primary and Secondary Effectiveness Endpoints. All patients enrolled and randomized in the study will be included in all analyses. Sensitivity analyses may be considered and will be described in the final Statistical Analysis Plan for the study. Nevertheless, the totality of the results will be used when evaluating overall Study Success.

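### The primary superiority test on opioid use is assigned only to a Per-Protocol cohort selected after randomization, and Sections 11.5 and 11.9 contradict each other on who is analyzed

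*Protocol*

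**What the plan says.** Section 11.2.1 of the protocol defines the primary test: "A superiority hypothesis test using the two-independent sample t-test will be used to statistically evaluate the difference in the average TME" at one-sided alpha 0.025. Whether the primary objective is met depends on this test.

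Section 11.3 defines two effectiveness cohorts. For the first, 11.3.2 states: "All subjects who are randomized are included in the Safety/ITT Cohort", with analysis by randomized group. The second, in 11.3.3, is limited to randomized subjects who got their assigned treatment and "who complete their 6-week visit without any major protocol deviations".

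Section 11.3.4 gives the primary endpoint to the second cohort alone: "Total Daily Morphine Equivalent, will be made using the Per-Protocol Cohort". Section 11.3.5 does the same for Change in WOMAC Pain, but not for the rest: "Analyses for all other secondary endpoints will be repeated using the Safety/ITT Cohort and the Per-Protocol Cohort".

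On missing data, 11.5 rules out imputation, so that "subjects missing results for a specific analysis will be excluded from that analyses". Section 11.9 also rules out imputation, yet adds: "All patients enrolled and randomized in the study will be included in all analyses". It leaves sensitivity analyses, as an option, to the SAP.

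**The concern.** A superiority claim rests on comparing groups as randomized. All three Per-Protocol conditions are met or failed after assignment. Completing the Week 6 visit and avoiding a major deviation can depend on pain and opioid use, and opioid use is the outcome. The withdrawal reasons in Section 10.10 include adverse events and a need for prohibited medication or treatment, both plausibly linked to pain. Exclusions may therefore be informative. If they differ between arms, the comparison of means is biased by an unknown amount in an unknown direction.

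The protocol already has the cohort this test needs and uses it for lesser endpoints, but not for the decisive one.

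The second problem is the conflict over who is analyzed. A subject with a major deviation and complete pill counts is out under 11.3.4 and in under 11.9. A subject with no primary result is out under 11.5 and in under 11.9, with no imputation to make that possible.

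**Working it through.** **The plan's own figure.** Section 11.10 gives an effect of 7.14 mg/day, SD 13.1, one-sided alpha 0.025 and power 0.80. The normal approximation is n = 2(1.96 + 0.84)² × (13.1/7.14)², which rounds up to 53 per group. The exact noncentral t gives 54 (power 80.1%). The stated 54 reproduces, so the point does not rest on a sample-size error.

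**Subjects available.** Section 11.10 randomizes 75 per arm and allows 10% loss: 75 × 0.90 = 67.5, so about 67 per arm.

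**Bias from selective exclusion.** The protocol gives no exclusion rates by arm, so these inputs are assumptions: true difference zero, a fraction q of an arm excluded, and excluded subjects using k × 13.1 mg/day more than retained ones. The retained mean then lies q × k × 13.1 below the full-arm mean. If exclusion is informative in the active arm only, the spurious advantage is that amount, and

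type I error = 1 − Φ(1.96 − bias/SE), with SE = 13.1 × √(1/n₁ + 1/n₂).

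For 67 per arm, SE = 13.1 × √(2/67) = 2.26. For 67 versus 75 it is 2.20, and for 67 versus 71 it is 2.23. The last case has heavier users excluded in both arms, so its bias is (0.10 − 0.05) × k × 13.1.

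| Assumed scenario | k = 0.5 | k = 1.0 | k = 1.5 |
|---|---|---|---|
| 10% excluded, informative in active only: bias, mg/day | 0.66 | 1.31 | 1.97 |
| Same, as a share of 7.14 | 9% | 18% | 28% |
| Type I error, 67 per arm | 4.7% | 8.4% | 13.7% |
| Type I error, sham keeps all 75 | 4.8% | 8.6% | 14.3% |
| Excluded subjects use less by the same amounts, 67 per arm | 1.2% | 0.6% | 0.2% |
| 10% active versus 5% sham: bias, mg/day | 0.33 | 0.66 | 0.98 |
| Type I error, 10% versus 5% | 3.5% | 4.8% | 6.4% |

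With equal exclusion of similar subjects in both arms the bias is zero and the error stays at 2.5%.

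**Power after the change** (noncentral t, one-sided 0.025, SD 13.1). If 10% of subjects have no benefit, the effect is 7.14 × 0.90 = 6.43.

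| Per arm | Effect, mg/day | Power |
|---|---|---|
| 75 | 7.14 | 91% |
| 67 | 7.14 | 88% |
| 75 | 6.43 | 85% |
| 67 | 6.43 | 81% |

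**The case against.** The strongest reply is that the illustration does not isolate the Per-Protocol choice. The only 10% in the protocol covers withdrawal and missing primary data, and 11.5 would remove those without data from an ITT-labelled analysis too. What Per-Protocol adds is subjects who did not receive their assigned treatment, major deviators with data, and those who missed Week 6 but have usable counts. The first group should be small, since Section 10.4 and the footnote to Table 3 place randomization before or at the single treatment visit. This stands as a limit on the numbers: the protocol does not allow the increment to be sized. It is also why the fix cannot stop at renaming the cohort.

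The active-only scenario is also severe. Section 9.1 describes tips of identical appearance, with identical lights and sounds. At k = 1.5 the excluded subjects use 1.5 × 13.1 = 19.65 mg/day more, which is 2.75 times the planned effect. That is fair, and the milder 10% versus 5% rows deserve equal weight. Blinding limits differential exclusion but does not rule it out, because a treatment that works can itself change who drops out or deviates.

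Third, 11.3.4 is the specific rule and 11.9 a general sentence under another heading, so most analysts would follow 11.3.4. That is probably true and makes divergent primary results less likely. The two sentences still conflict, and the rule most would follow is the one that is unsuited to a superiority test.

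Finally, the SAP may add an ITT sensitivity analysis. That would help, but the protocol would still fix Per-Protocol as primary.

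**Conclusion.** The concern holds. The protocol itself fixes a post-randomization subset as the only cohort for its decisive superiority test, so this is not a detail left to the SAP. Section 11.9 is incompatible with both 11.3.4 and 11.5.

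The consequence is loss of protection rather than a demonstrated bias. The type I error figures show what modest selective exclusion could do in either direction. They rest on assumed exclusion rates and usage differences, and they combine Per-Protocol with missing-data exclusions. The conflict between sections rests on the text alone and needs no assumption. Both parts should be settled before unblinding.

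**What to change.** - In 11.3.4, name the Safety/ITT Cohort, analyzed as randomized, as the primary cohort for TME, with Per-Protocol as supportive.
- Reconcile 11.3.4, 11.5 and 11.9 into one rule on who is analyzed.
- Because a cohort change alone does not recover subjects dropped under 11.5, have that rule say how the Week 2 and Week 4 counts are used when the Week 6 count is missing. Section 10.7.1 already collects them: "A pill count will be completed by the study coordinator, or designee, and opioid medication will be redispensed to subjects". The method can be left to the SAP.
- State, in the protocol or the SAP, that major deviations are classified before unblinding. This is advisable, but the finding does not depend on it.
- For the WOMAC Pain non-inferiority test, Per-Protocol may stay, with the ITT result reported alongside.

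The cost is wording in three sections, with no new data, visits or subjects. The price is possible dilution of the estimate. In the most cautious case computed above (10% without benefit and 67 per arm with data), power still meets the planned 80%.
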